6.1.1 Lost to Follow Up

Every reasonable effort is to be made to contact any subject lost to follow-up during the course of the study to complete study-related assessments and record outstanding data.

6.2 Discontinuation of the Site

If an investigator intends to discontinue participation in the study, the investigator must immediately inform the sponsor.

02 Dec 2019 Astellas Page 68 of 111

6.3 Discontinuation of the Study

The sponsor may terminate this study prematurely, either in its entirety or at any study site, for reasonable cause provided that written notice is submitted in advance of the intended termination. Advance notice is not required if the study is stopped due to safety concerns. If the sponsor terminates the study for safety reasons, the sponsor will immediately notify the investigator and subsequently provide written instructions for study termination.

7 STATISTICAL METHODOLOGY

A statistical analysis plan (SAP) will be written to provide details of the analysis, along with specifications for tables, listings and figures to be produced. The SAP will be finalized before the database soft lock at the latest. Any changes from the analyses planned in SAP will be justified in the clinical study report.

In general, continuous data will be summarized with descriptive statistics (number of subjects, mean, standard deviation, geometric mean and geometric standard deviation (GSD) where applicable, minimum, median and maximum), and frequency and percentage for categorical data. Percentages by categories will be based on the number of subjects with no missing data, i.e., the percentages will sum to 100%.

Baseline will be defined as the last observation prior to first dose, unless otherwise specified.

7.1 Sample Size

In Stage 1, approximately 120 evaluable adults 18 to 64 years of age are planned to be enrolled. This sample size in is considered sufficient to obtain preliminary estimates in a phase 1 study of safety and reactogenicity in the adult population, ages 18 to 64. In Stage 2, approximately 495 evaluable adult subjects from 65 to 85 years of age are planned to be enrolled. For each PCV13 serotype the OPA titer⁻¹ responses (geometric mean titer [GMT] and GSD) in subjects 60 to 64 years of age administered PCV13 (Source Prevnar13[®] label) were assumed to be representative of the response following immunization with ASP3772. The width of 95% confidence intervals for each serotype with 30, 100 and 150 subjects were calculated. A sample size of 100 subjects at each dose level treated with ASP3772 under these assumptions was considered sufficient to provide good estimates of OPA titer⁻¹ responses. The sample size and dose level for the phase 3 study will be determined based on the responses in Stage 2 elderly subjects.

7.2 Analysis Sets

The Safety Analysis Set (SAF) will consist of all subjects who receive an immunization in this study with either ASP3772, PCV13, or PPSV23. The Full Analysis Set (FAS) will consist of all subjects who receive an immunization in this study with either ASP3772, PCV13 or PPSV23 and have at least 1 postimmunization measurement.

For each ASP3772, PCV13 or PPSV23 immunization group, the number and percentage of subjects in each analysis set will be given for all randomized (ASP3772 or PCV13) or enrolled (PPSV23) subjects.

O2 Dec 2019 Astellas Page 69 of 111

7.2.1 Full Analysis Set (FAS)

The FAS will be used for summaries and primary analyses of immunogenicity data.

7.2.2 Per Protocol Set (PPS)

The PPS will be used to assess immunologic response and will serve as a supportive analysis. The PPS will exclude the following subjects:

- Subjects who are given antibiotics within 7 days prior to the 30-day blood draw to assess immunogenicity in the ASP3772 immunization group since these may interfere with the immunogenicity assay
- Subjects who have their 30-day blood draw 14 or more days after the 30 day post immunization scheduled blood collection
- Subjects who receive immunosuppressants as this may interfere with their ability to mount a response to the vaccine
- Subjects who have newly diagnosed immunologic abnormalities within the first 2 weeks after receiving the immunization.

7.2.3 Safety Analysis Set (SAF)

The SAF will be used for most summaries of demographic and baseline characteristics and all safety and tolerability related variables. There are a limited number of displays that will use all subjects who gave informed consent or all subjects who were randomized.

7.3 Demographics and Baseline Characteristics

Demographics and baseline characteristics (age, sex, race, ethnicity, weight, height and body mass index) will be summarized by dose cohort and immunization group (ASP3772 or PCV13) and for all PCV13 subjects combined. Summaries will be given separately for the adults (18 to 64 years) and elderly (65 to 84 years). A summary will be provided for the PPSV23 enrolled subjects.

7.3.1 Subject Disposition

Disposition (consented, discontinued before randomization, randomized, vaccinated) will be provided by stage (adults, elderly), dose cohort (1 μ g, 2 μ g, 5 μ g) and immunization group (ASP3772 or PCV13) and for all PCV13 subjects combined. A summary will be provided for the PPSV23 enrolled subjects.

The number and percentage of subjects who completed the study, those who discontinued the study and the reasons for study discontinuation (AE, death, lost to follow-up, protocol deviation, withdrawal by subject, non-compliance with study, other) will be presented for SAF subjects for each stage (adults, elderly). All disposition details and dates of first and last evaluations for each subject will be listed.

7.3.2 Previous and Concomitant Medications

All previous and concomitant medications for each subject will be listed.

02 Dec 2019 Astellas Page 70 of 111

7.3.3 Medical History

Medical history for each subject will be listed.

7.4 Analysis of Immunogenicity

Assessment of immunological response following ASP3772 administration relative to PCV13 is a secondary objective for this study.

Stage 1:

The following measures in adults 18 to 64 years of age will be used to characterize the immunological response 30 days following administration of either ASP3772 or PCV13. These measures will be provided for each immunization group (PCV13 vs ASP3772) and dose level (ASP3772: 1, 2, 5 µg).

- The GMT, GSD and 95% confidence interval (CI) for functional OPA for each serotype will be calculated.
- The ratio of the OPA GMT (each ASP3772 dose level/PCV13) and 95% CI will be provided.
- The geometric mean concentration (GMC), GSD and 95% CI for serotype-specific IgG for each of the serotypes will be calculated.
- The ratio of the IgG GMC (each ASP3772 dose level/PCV13) and 95% CI will be provided.
- The GMFR, GSD and 95% CI in anticapsular polysaccharide IgG and OPA titer will be calculated for each of the serotypes unique to ASP3772.
- The proportion of subjects with $a \ge 4$ -fold increase in anticapsular polysaccharide IgG and OPA relative to baseline will be calculated.

Stage 2 Group 2:

The following measures in adults 65 to 84 years of age will be used to characterize the immunological response 30 days following vaccine administration. These measures will be provided by dose cohort for ASP3772 and for PCV13 as a single group for each serotype.

- The GMT, GSD and 95% CI for functional OPA activity for each serotype will be calculated.
- The ratio of the GMT for functional OPA (each ASP3772 dose level/PCV13) for each serotype and the 95% CI will be provided.
- The GMC, GSD and 95% CI for serotype-specific IgG for each of the serotypes will be calculated.
- The ratio of the IgG GMC (each ASP3772 dose level/PCV13) and 95% CI will be provided for each serotype.
- The GMFR, GSD and 95% CI in anticapsular polysaccharide IgG and OPA titer will be calculated for each of the serotypes unique to ASP3772.
- The proportion of subjects with $a \ge 4$ -fold increase in anticapsular polysaccharide IgG and OPA relative to baseline will be calculated
- To assess the impact of ASP3772 dose, an analysis of covariance (ANCOVA) model with age (65 to 74 years, 75 to 85 years) as the covariate and immunization (ASP3772 1,

02 Dec 2019 Astellas Page 71 of 111

2, 5 μ g or PCV13) as the factor of interest will be conducted on the natural logarithm (log) of pneumococcal OPA titers and the natural log of the IgG concentrations.

In addition, for both Stage 1 Group 1 and Stage 2 Group 2, SP1500+0785 levels (ng/mL) will be collected for those subjects given either ASP3772 or PCV13. Levels of the following cytokines will be collected for subjects given ASP3772 or PCV13: Th17, IL-17, IL-17, IL-22, The units for all are pg/mL. Non-parametric methods will be used for these analyses. A Kruskal-Wallis test will be used to test for overall differences between the 3 dose levels and PCV13. All treatment groups in Stage 1 will be compared, followed by paired comparisons between each of the ASP3772 dose levels and PCV13 using a Wilcoxon Test. The same set of comparisons will be made for subjects in Stage 2, Group 2.

Stage 2; Group 3:

For the 11 serotypes contained in PPSV23 and not in PCV13, immunological response will be evaluated by the following endpoints at 30 days after administration of PPSV23:

- The GMFR, GSD and 95% CI in anticapsular polysaccharide IgG and OPA titer
- The proportion of subjects with a ≥ 4-fold increase in anticapsular polysaccharide IgG and OPA relative to baseline
- The GMT, GSD and 95% CI for the OPA titers
- The GMC, GSD and 95% CI for serotype-specific IgG levels.

7.5 Analysis of Safety

Safety and tolerability of ASP3772 are the primary objectives in Stage 1 and Stage 2 of this study and will be assessed by:

- TEAEs (including SAEs, MAAEs, PIMCCs and NOCDs)
- Laboratory assessments
- Vital signs (body temperature, blood pressure and pulse rate)
- Physical examination
- ECG
- Reactogenicity

Safety analyses will be performed on the SAF; all subjects who receive study immunization. Data from PCV13 subjects in each cohort will be pooled.

For each local and systemic solicited reaction the percentage of subjects who reported each symptom by grade (None, Grade 1, 2, 3 or 4) will be summarized (n, %) by immunization group (PCV13 vs ASP3772) and dose level (ASP3772: 1, 2, 5 µg) and the percentage of subjects who reported any symptom.

02 Dec 2019 Astellas Page 72 of 111

7.5.1 Adverse Events

A TEAE is defined as an AE observed after study immunization and up to 30 days postimmunization. SAEs will be monitored for up to 180 days postimmunization (Group 1 and Group 2).

For each immunization arm, the frequencies and percentages will be displayed for the following TEAEs (coded using the Medical Dictionary for Regulatory Activities [MedDRA]) by system organ class and preferred term:

- Overall
- Serious
- Related (yes or no) to study vaccine

The number and percentage of subjects with TEAEs, SAEs, AEs and AEs related to study vaccine will be summarized by system organ class, preferred term and immunization group. The number and percentage of AEs by severity will also be summarized. MAAEs including PIMMCs and NOCDs, if any, will be summarized. All AEs will be listed.

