Visit Days (Window)	-28 to -3	1	7 (+1)	30 (±2)*	180 (±14)§
Informed Consent ^b	X				
Inclusion/Exclusion Criteria	X	X†			
Randomization ^c		X†			
Demographics	X				
Medical History ^d	X	Χţ			
Physical Examination ^e	X	X†		X	
Routine 12-lead ECG	X	Χţ	X	X	
Virology ^f	X				
Urine Drug Screen ^g	X	X†			
Pregnancy Test ^h	X	X†		X	
Height, Body Weight	X				
Study Immunization		X			
Vital Signs (blood pressure, pulse rate, body temperature) ⁱ	X	X†	X	X	
Clinical Laboratory Tests (hematology biochemistry, coagulation profile, hepatic profile, urinalysis) ^j	X	X†‡	X	X	
Serum sample for Immunogenicity		Χţ		X	
Serum sample for Anti-biotin Antibodies		X†		X	X^{l}
Whole-blood sample for T-cell Immune Response Measurement		Χţ	X	X	
Prior/Concomitant Medication ⁿ				\rightarrow	
Reactogenicity ^o		<	\longrightarrow		
AEsp					
SAEs ^p	<				
MAAEs including PIMMCs and NOCDs ^p		<			\longrightarrow

AE: adverse event; ECG: electrocardiogram; MAAE: medically attended adverse event; NOCD: new-onset chronic disease; PIMMC: potential immune-mediated medical conditions; SAE: serious adverse event; WBC: white blood cell.

Footnotes continued on next page

02 Dec 2019

Astellas

Page 29 of 111

- CONFIDENTIAL -
- † To be performed prior to administration of study vaccine. **Note:** Vital signs will also be performed after the administration of the study vaccine.
- \ddagger Not required if collected at a screening visit, which is ≤ 7 days from dosing visit.
- § Visit conducted as a phone call unless anti-biotin antibodies were elevated at day 30 visit.
- * If a subject has received any systemically absorbed antibiotics between day 1 and day 30, the visit should take place at least 7 days after the last dose of the antibiotics.
- a. Screening will be completed up to 28 days prior to study immunization. Subjects will be assigned a subject number for use throughout the study at the screening visit via the Interactive Response Technology (IRT) system
- b. Informed consent must be obtained prior to the performance of any study-related procedure and before Randomization.
- c. Subjects will be randomized via the IRT at the dosing visit.
- d. Medical history will be collected at screening in order to assess Inclusion/Exclusion criteria and will be reconfirmed prior to study immunization.
- e. A physical examination will be performed at the screening visit (days -28 thru -3), prior to study immunization (day 1) and day 30 visits.

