- f. Perform tests for Hepatitis B surface antigen (HBsAg), hepatitis B core antibody, hepatitis A virus antibodies (immunoglobulin M), HCV antibody (anti-HCV) confirmed by reflex testing (HCV-RNA) and HIV antigen/antibody (type 1 and/or type 2) at screening.
- g. Perform screening test for amphetamines, barbiturates, benzodiazepines, cannabinoids, cocaine and opiates at screening visit. Repeat urine drug screening before study immunization.
- h. Serum pregnancy test will be done at the screening visit. Urine pregnancy test will be done at study immunization (day 1) and day 30 visits. Not necessary for female subjects who are not of childbearing potential (e.g., post-menopausal [defined as at least 1 year without any menses] or documented surgically sterile) at screening and dosing visit.
- i. Body temperature, blood pressure and pulse rate will be assessed in a sitting position. At the dosing visit, body temperature, blood pressure, pulse rate and respiratory rate will be assessed predose and approximately 30 min and 1 hour postdose. Predose vital signs should be collected close to the vaccination and should not be more than 30 minutes prior to the dose administration. Body temperature will be collected by the subject daily through day 7 following the study immunization.
- j. Perform test for hematology (hemoglobin, hematocrit, erythrocytes, leukocytes, differential WBC, platelets), biochemistry (sodium, potassium, calcium, chloride, glucose, total cholesterol, triglycerides, blood urea nitrogen, creatinine, total protein, albumin, c-reactive protein), coagulation profile (prothrombin time, activated partial thromboplastin time, fibrinogen), hepatic profile (alkaline phosphatase, aspartate transaminase, alanine transaminase, γ-glutamyltransferase, total bilirubin, lactate dehydrogenase), urinalysis (using dipstick protein, glucose, pH, blood, leukocytes, urobilinogen, bilirubin, ketones, nitrite, urine microscopy [optional]).
- k. CCI
- 1. Sample collection to test for serum anti-biotin antibodies should be repeated at the day 180 visit if tested positive on day 30. Biotin levels will be measured in the same sample if the sample is positive for anti-biotin.
- Please see Laboratory Manual for more details.
- n. All concomitant medications or therapies administered from the time the informed consent form (ICF) is signed through day 30 follow up visit will be collected. *Footnotes continued on next page*

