5.4 Safety Assessment

5.4.1 Adverse Events

All observed or spontaneously reported AEs will be documented. TEAEs and MAAEs (including PIMMCs and NOCDs) will be assessed throughout the study, from the time of dosing (day 1) up to the last follow-up visit (day 30 for Group 3; day 180 for Groups 1 and

02 Dec 2019 Astellas Page 56 of 111

2). Details of definitions and reporting of AEs (including TEAEs, MAAEs, PIMMCs and NOCDs) and SAEs are provided in [Section 5.5 Adverse Events and Other Safety Aspects].

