5.5 Adverse Events and Other Safety Aspects

5.5.1 Definition of Adverse Events

An AE is any untoward medical occurrence in a subject administered a study vaccine, and which does not necessarily have to have a causal relationship with this immunization. An AE can therefore be any unfavorable and unintended sign (including an abnormal laboratory finding), symptom, or disease (new or exacerbated) temporally associated with the use of a medicinal product whether or not considered related to the medicinal product.

In order to identify any events that may be associated with study procedures and could lead to a change in the conduct of the study, Astellas collects AEs even if the subject has not received study product. AE collection begins after the signing of the ICF and will be collected until 30 days after study vaccine administration or the subject is determined to be a screen failure.

Care will be taken not to introduce bias when detecting AEs and/or SAEs. Open-ended and non-leading verbal questioning of the subject is the preferred method to inquire about AE occurrences.

An abnormality identified during a medical test (e.g., laboratory parameter, vital sign, ECG data, physical exam) should be identified as an AE only if the abnormality meets 1 of the following criteria:

- Induces clinical sign or symptoms
- Requires active intervention
- Requires interruption or discontinuation of study medication
- The abnormality or investigational value is clinically significant in the opinion of the investigator.

MAAEs are AEs for which the subject has received medical attention by medical personnel, or in an emergency room, or which led to hospitalization. For each reported AE, the investigator will ask the subject if such medical attention has been received. In addition, the investigator will assess each MAAE if it constitutes a new-onset chronic disease (NOCD), defined as a MAAE which a) was absent at baseline, b) is not resolved at the follow-up telephone call, c) requires continuous medical care or attention. The investigator will also assess if any MAAE constitutes a PIMMC. PIMMCs are defined as any AEs of autoimmune

02 Dec 2019 Astellas Page 59 of 111

or auto inflammatory nature. The investigator will record MAAEs, NOCDs and PIMMCs in the AE eCRF.

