5.5.5 Reporting of Serious Adverse Events (SAEs)

The collection of AEs will continue until 30 days after study vaccine administration in all groups. The expedited reporting of SAEs will start following receipt of the ICF and will continue until 180 days after study vaccine administration in Groups 1 and 2 and until 30 days after study vaccine administration in Group 3, or until the subject is determined to be a screen failure or withdraws from the study.

In the case of an SAE, the investigator must contact the sponsor by fax or email immediately (within 24 hours of awareness).

The investigator must complete and submit an SAE worksheet containing all information that is required by local and/or regional regulations to the sponsor by email or fax immediately (within 24 hours of awareness).

The SAE worksheet must be signed by a medically qualified investigator (as identified on Delegation of Authority Log). Signature confirms accuracy and completeness of the SAE data as well as the investigator causality assessment including the explanation for the causality assessment.

If the SAE is associated with emergency unblinding as outlined in [Section 4.4.4 Breaking the Study Vaccine Assignment Code for Emergency], this is to be recorded on the SAE

02 Dec 2019 Astellas Page 62 of 111

worksheet. Within the SAE worksheet, the investigator is to include when unblinding took place in association with the SAE.

For contact details, see [Section II Contact Details of Key Sponsor's Personnel]. Fax or email the SAE/Special Situations Worksheet to:

Astellas Pharma Global Development – United States
Pharmacovigilance
[contact]
Email: [contact]

The following minimum information is required:

- International Study Number/Study number,
- Subject number, sex and age,
- The date of report,
- A description of the SAE (event, seriousness criteria),
- Causal relationship to the study vaccine (including reason), and
- The drug provided (if any) (blinded regimen is also an option)

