6.2.1.1 Adverse Events

AE collection begins after the ICF has been signed and continues until screen failure, or for those enrolled, 30 days after study vaccine administration. A TEAE is defined as an AE observed after study immunization and up to 30 days post immunization. Medically attended adverse events (MAAEs) are AEs for which the subject has received medical attention by medical personnel, or in an emergency room, or which led to hospitalization. A new-onset chronic disease (NOCD), is defined as a MAAE which a) was absent at baseline; b) has not resolved at the follow-up telephone call; c) requires continuous medical care or attention.

PIMMCs are defined as any AEs of autoimmune or auto inflammatory nature. SAEs, MAAEs, which include PIMMCs and NOCDs, will be collected throughout the study, from vaccine administration on Day 1 up to the last follow-up visit (day 30 for Group 3; day 180 for Groups 1 and 2).

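### The TEAE window closes 30 days after vaccination, but a compliant Day 30 safety visit can fall later, and the documents disagree on when safety collection ends

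*Protocol*

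**What the plan says.** TEAEs are among the primary endpoints (Protocol 2.3, SAP 6.2.1). Protocol 7.5.1 and SAP 6.2.1.1 define them alike; the protocol wording is "A TEAE is defined as an AE observed after study immunization and up to 30 days postimmunization". General AE collection has the same end: Protocol 5.5.1 says "AE collection begins after the signing of the ICF and will be collected until 30 days after study vaccine administration", and Protocol 5.5.5 says "The collection of AEs will continue until 30 days after study vaccine administration in all groups".

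The last scheduled physical examination, ECG, vital signs and laboratory tests are at the Day 30 visit, window ±2 days, with vaccination on Day 1 (Protocol Tables 1 to 3). The Group 1 and Group 2 schedules add a deferral: "If a subject has received any systemically absorbed antibiotics between day 1 and day 30, the visit should take place at least 7 days", counted from the final antibiotic dose. Protocol 5.1.3 and Appendix 12.4 give the same rule without limiting it to a group. No upper limit is set.

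Other text runs to the visit rather than to a count of days. Concomitant medications "through day 30 follow up visit will be collected" (Table 1, footnote n, with matching footnotes in Tables 2 and 3). Protocol 5.4.1 says "TEAEs and MAAEs (including PIMMCs and NOCDs) will be assessed throughout the study, from the time of dosing (day 1) up to the last" scheduled contact, which it gives as Day 30 for Group 3 and Day 180 for Groups 1 and 2. For Group 3 SAEs, Protocol 5.5.5 stops 30 days after vaccination, while SAP 6.2.1.1 collects SAEs and MAAEs to the last follow-up visit.

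**The concern.** The Day 30 visit is the planned means of finding laboratory, ECG and examination abnormalities after Day 7. If it can properly take place after the TEAE window has closed, a finding made there may be left out of the primary safety tables although the site followed the protocol exactly. The longer overruns fall on subjects treated with antibiotics near Day 30, that is, subjects with an intercurrent illness, so the omission would not be random with respect to health. Laboratory and TEAE tables could also disagree about the same subject. Because different sections give different ends for the same endpoint, the programming would depend on which section was followed.

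**Working it through.** **Inputs.** Vaccination is on Day 1. The visit window is Days 28 to 32 (Protocol Tables 1 to 3). The deferral is at least 7 days after the last antibiotic dose. The TEAE limit is 30 days. The SAP analysis window for the Day 30 visit is Day 16 to Day 46 (SAP 7.7.3). The plan gives no figure of its own to reproduce.

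**Day count.** Two numerical readings of the limit are possible:
- Elapsed days: days after dosing = study day − 1, so the window ends on Day 31 (31 − 1 = 30).
- Nominal: the window ends on study Day 30.

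**Ordinary visit window.** On the elapsed reading only Day 32 is outside (32 − 1 = 31 days, 1 day over). On the nominal reading Days 31 and 32 are outside (1 and 2 days over).

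**After antibiotics.** Earliest visit = max(Day 28, last dose day + 7).

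| Last antibiotic dose | Earliest visit | Days past window, elapsed | Days past window, nominal |
|---|---|---|---|
| Day 23 or earlier | Day 30 or earlier | 0 | 0 |
| Day 24 | Day 31 | 0 | 1 |
| Day 25 | Day 32 | 1 | 2 |
| Day 26 | Day 33 | 2 | 3 |
| Day 27 | Day 34 | 3 | 4 |
| Day 28 | Day 35 | 4 | 5 |
| Day 29 | Day 36 | 5 | 6 |
| Day 30 | Day 37 | 6 | 7 |

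A course running past Day 30 pushes the visit later still. The SAP assigns visits to Day 30 up to Day 46, which is 46 − 31 = 15 or 46 − 30 = 16 days past the TEAE window.

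**One subject traced through the sections.** Suppose antibiotics end on Day 26, the visit is on Day 33, and a clinically significant platelet count is first seen there, non-serious and not medically attended.
- Protocol 5.5.1.1 makes it reportable as an unsolicited AE, with no 30-day limit. Protocol 5.4.6 does the same for new examination findings.
- Protocol 5.5.1 and 5.5.5 have already ended AE collection.
- SAP 7.7.3 places the value in the Day 30 laboratory summary and does not exclude data for visit timing.
- Protocol 7.5.1 and SAP 6.2.1.1 leave it out of the TEAE tables: Day 33 is 32 days after dosing.
- Protocol 5.4.1 places it inside the TEAE assessment period.

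**Onset or detection.** The definition turns on when an AE is observed and does not say which date governs. If onset governs, a symptom that began by the cut-off and is reported late still counts, and an entirely missing onset date is imputed to the dosing date (SAP 7.7.4). A laboratory or ECG abnormality first found at the late visit has no earlier date, so an onset rule does not clearly bring it in.

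**The case against.** The strongest reply is that the limit was meant as the visit itself. The protocol synopsis describes follow-up at 7, 30 and 180 days after immunization, so 30 days can be read as the name of the visit. That is plausible for the TEAE definition. It fits less well with 5.5.1 and 5.5.5, which count from vaccine administration, and no section says it. The objection shows that the wording is ambiguous; it does not settle it.

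A reader might infer that findings at a late visit cannot count as TEAEs and are lost. The documents do not support that. Protocol 5.4.1 points the other way, 5.4.6 and 5.5.1.1 still require recording, 7.5.1 lists all AEs, and laboratory values and vital signs are summarised in their own right. In Groups 1 and 2, SAEs and MAAEs are collected to Day 180, and Protocol 5.5.6 requires later (S)AEs to be notified when a relationship is reasonably possible. A listing is still not the primary summary, so the narrower point remains.

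Nor is the AE cut-off the only one stopping at Day 30: the liver-test maxima in SAP 7.5.3.2 also run through Day 30. A delay of a week beyond Day 30 is forced only when the last antibiotic dose is on Day 30 or later.

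It also counts against a large effect that the window is the same in all randomised arms, that AE analyses are descriptive, and that escalation within a stage rests on Day 7 data. A fixed window does give every subject equal time at risk, which is a fair argument for keeping it as a secondary display.

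**Conclusion.** The mismatch is real but modest. Under Protocol 7.5.1 and SAP 6.2.1.1, a non-serious abnormality first dated to a compliant Day 32 visit, or to a visit deferred for antibiotics, falls outside the TEAE summaries while its laboratory value appears under Day 30. Protocol 5.4.1 contradicts that definition, and Protocol 5.5.5 and SAP 6.2.1.1 differ on the end of Group 3 SAE collection, where this visit is the last contact.

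The overrun is 1 to 2 days within the ordinary window. After antibiotics the forced overrun is 2 to 6 days (elapsed) or 3 to 7 days (nominal) for last doses on Days 26 to 30. It is tempting to take one or two of the five permitted days as one or two fifths of the 615 planned subjects (120 + 396 + 99), giving 123 or 246. That assumes evenly spread visits, and the documents give no visit-timing, antibiotic-use or late-finding rates. The number affected cannot be computed and is probably small. The conclusion rests on reading the 30 days as a count of days; if the visit was meant, the text should say so.

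**What to change.** Reconcile Protocol 5.4.1, 5.5.1, 5.5.5 and 7.5.1 with SAP 6.2.1.1:

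- End general AE collection and the TEAE window at the later of 30 days after vaccination and the actual Day 30 visit (Visit 4 in Groups 1 and 2, Visit 3 in Group 3).
- State whether onset or detection date decides whether an event is a TEAE, and which date applies to an abnormality first found by a test.
- In Protocol 5.4.1, give TEAEs this same end and keep Day 180 for SAEs and MAAEs, including PIMMCs and NOCDs, in Groups 1 and 2.
- In Protocol 5.5.5, align the Group 3 end for SAEs and MAAEs with the last follow-up visit, as in SAP 6.2.1.1.

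The cost is a short wording change in five sections. The rule never shortens the 7.5.1 window and matches how concomitant medications are collected. Its drawback is that the window varies slightly between subjects and is longer after an antibiotic deferral. Showing the strict 30-day count in a footnote keeps the equal-time comparison available.
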